Treatment groups will be dummy coded with CC (coping control) used as the reference group. We will test for treatment condition effects on the stress and symptom outcome measures using MLMs as we did in our publications in the R21 feasibility trial. MLMs provide an optimal analytic strategy because they model all available data (following intent-to-treat principles in RCTs) and allow us to flexibly evaluate the nested nature of this data structure. Specifically, we will create (for EMA) 3-level MLMs (levels: individual participants; day; within-day time) using restricted maximum likelihood estimation. The 3-level EMA MLMs testing each aim will compare the 3 treatment intervention groups on each dependent variable (e.g., daily stress) from the pre, post, and follow-up training measurement occasion. The 3-level models will include a random intercept for day nested within participant. Measurement occasion (pre, post intervention, follow-up), group condition, day-specific factors (e.g., day-of-week or weekday versus weekend), and within-day time will be modeled as fixed effects. All models will be fit with compound symmetric variance-covariance data structure but other structures (e.g., autoregressive covariance structure, ARH(1), spectral power) will be evaluated using Akaike's Information Criterion (AIC). We have specified this initial approach for modeling random and fixed effects, but we will evaluate whether this approach best fits the data using likelihood ratio tests and AIC. In testing each aim, each measurement occasion  $\times$  treatment interaction will be evaluated with a decision rule that a significant effect is observed when the measurement occasion  $\times$  treatment interaction statistic and corresponding p-value is less than .05 (two-tailed). When a significant interaction is observed, follow-up planned contrasts in each MLM will compare specific groups at post-training. To help with benchmarking we will provide effect size statistics corresponding to the magnitude of change over time, and between groups at each post-treatment time point. One strength of our approach here is that it extends an established MLM data analytic pipeline we used in our three-arm EMA R21 trial publications with success, along with MLM mediation analyses in other MBSR RCT publications.

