**Testing our Hypotheses.** We are specifying a priori predictions about the effects of MA-MBSR intervention, relative to MO-MBSR and CC. Thus no statistical corrections for multiple comparisons will be made for our primary study hypotheses or specified pair-wise comparisons. When additional exploratory analyses are conducted, a Holm's correction will be made for multiple comparisons. We have previously published our MLM approach evaluating MA-MBSR effects relative to these two control groups (see Chin et al., 2019 or Lindsay et al., 2018 publications)—so here we highlight our equations and approach. In previous work we have focused on stress, so below we apply this approach to evaluating hypothesis #2, specifying that MA-MBSR will reduce symptoms relative to MO-MBSR and CC. This hypothesis will be tested separately for clinician assessed, physician assessed or patient self-reported symptoms (using the IBS-SS). The general form of the model to be tested, exclusive of covariates, is as follows, in mixed model

notation:

IBS symptomsit =  $\gamma_{00} + \gamma_{01} \cdot (\text{txgroup}_i) + \gamma_{10} \cdot (\text{time}_{it}) + \gamma_{11} \cdot (\text{txgroup}_i) \cdot (\text{time}_{it}) + u_{0i} + e_{it}$  where IBS symptomsit is the composite symptoms score for individual  $i$  at time-point  $t$ , timeit is the measurement occasion (pre, post intervention, or follow-up) assessment time of year, txgroupi is the treatment group a participant is assigned to. In multilevel notation:

$$\begin{aligned} \text{Level 1: } & \text{Symptoms}_{it} = \beta_{0i} + \beta_{1i} \cdot (\text{time}_{it}) + e_{it} \\ \text{Level 2: } & \beta_{0i} = \gamma_{00} + \gamma_{01} \cdot (\text{txgroup}_i) + u_{0i} \\ & \beta_{1i} = \gamma_{10} + \gamma_{11} \cdot (\text{txgroup}_i) \end{aligned}$$

The primary test of hypothesis is the F-test of the null hypothesis  $H_0: \gamma_{11} = 0$ . Note that this general model will be used, with different outcomes (e.g., stress) and for subsequent aims below but will not be repeated.

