For hypothesis #3, we will use EMA-sampled IBS symptom severity to test whether EMA-sampled stress reduction will statistically mediate symptom improvements. We will test for concurrent relations between EMA-sampled stress and IBS symptom severity (within the same moment) and also test lagged relations (stress at time  $t$  predicting IBS symptom severity at time  $t+1$ ). To conduct this mediation analysis, we will compare two MLMs that use IBS symptom severity as the outcome and group condition as a fixed effect: one MLM will include stress as an additional fixed effect, and another will not. If the fixed effect for group condition is statistically significant in the latter but not the former, stress reduction will be declared to act as a mediator for symptom improvements.

For hypothesis testing, we will first run unadjusted models without covariates, as described above. Then, as a sensitivity analysis, we will run adjusted models that incorporate baseline characteristics related to sociodemographic covariates (sex, gender, age, race), clinical covariates (IBS subtype, baseline IBS symptom severity, baseline perceived stress), and other time-related covariates such as day-of-week when appropriate (e.g., for analyses involving EMA samples where we observe repeated measures across and within days).

**Attrition and Missing Data.** We expect minimal participant attrition (<15%) during the study period across conditions. Dropouts are not expected to be a function of the missing outcome data given the observed. Our unadjusted analyses assume data are missing completely at random, while our adjusted analyses loosen this assumption to allow for data to be missing at random. We will also assess the sensitivity of our results to violations of the missing-at-random assumption (e.g., via pattern-mixture models). Additionally, we will evaluate whether adherence to the program and EMA vary across groups. To evaluate attrition, we will compare study dropouts to study completers based on observed participant characteristics.

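### The hypothesis 3 mediation rule reads the group-condition effect, not the occasion × treatment interaction that the SAP uses as its treatment effect

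*SAP*

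**What the plan says.** Under Testing our Hypotheses, the aim for hypothesis 3 is to "test whether EMA-sampled stress reduction will statistically mediate symptom improvements". The method is that "we will compare two MLMs that use IBS symptom severity as the outcome and group condition as a fixed effect"; stress is a further fixed effect in one model and absent from the other. The rule begins "If the fixed effect for group condition is statistically significant in the latter but not the former", where the latter is the model without stress; if that holds, stress is declared a mediator. The paragraph names no occasion term and no interaction, and does not limit the analysis to prompts after training.

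Elsewhere the SAP takes its treatment effect from another term. Under Overview of Data Analyses, the EMA models compare the arms using data "from the pre, post, and follow-up training measurement occasion", and "each measurement occasion $\times$ treatment interaction will be evaluated with a decision rule" that requires "interaction statistic and corresponding p-value is less than .05 (two-tailed"). For the general model under Testing our Hypotheses, "The primary test of hypothesis is the F-test of the null hypothesis" that γ11, the group-by-time coefficient, is zero. The group coefficient γ01 is a separate term and is not the one tested. The same section adds: "Note that this general model will be used, with different outcomes (e.g., stress) and for subsequent aims below but will not be repeated".

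**The concern.** Stress reduction and symptom improvement are changes from the pre-training level, and no arm has been treated when the pre-training prompts are collected. A group coefficient fitted across all occasions is therefore not the difference in change between arms. Depending on how the model is completed, it is either an average that includes an untreated period or the untreated difference itself.

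The first step of the rule needs this coefficient to be significant before stress enters. If it falls short because it is diluted, mediation cannot be declared even when the trial has shown a treatment benefit on the interaction. The two parts of the plan could then disagree about whether there is any effect to mediate. This is separate from whether loss of significance is a sound test of mediation: a better method applied to the same coefficient would still decompose the wrong effect.

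**Working it through.** The SAP gives no sample size, effect size, correlation between occasions or coding of occasion, so there is no stated figure to reproduce. The inputs below are assumptions unless a source is named.

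**Inputs.** Three occasions (pre, post, follow-up) and a two-sided .05 level, both from Overview of Data Analyses. Assumed: a contrast of two arms with n per arm; the same number of prompts per occasion; person-by-occasion means with equal variance (set to 1) and common correlation r; a true arm difference of (0, d, d) if persistent or (0, d, 0) if post-only.

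**Step 1: what the group coefficient estimates.**

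| Completion of the model | Persistent effect | With d = 0.50 SD |
|---|---|---|
| Group, no interaction | (0 + d + d)/3 = 2d/3 | 0.333 |
| Interaction kept, occasion categorical, pre as reference | pre-training difference = 0 | 0.000 |
| Interaction kept, occasion sum-coded | 2d/3 | 0.333 |
| Interaction kept, linear time 0, 1, 2 | 2d/3 − d/2 = d/6 | 0.083 |

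In the last row the least-squares slope of (0, d, d) on time is d/2 and the mean time is 1. For a post-only effect the pooled coefficient is (0 + d + 0)/3 = d/3, or 0.167 with d = 0.50. None of these equals d, the value of the change-from-pre contrast.

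**Step 2: power of the pooled group test.** Expected z per unit of d, apart from the common factor √(n/2):

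- Pooled group effect: f / √((1 + 2r)/3), with f = 2/3 (persistent) or 1/3 (post-only).
- Change contrast, mean of post and follow-up minus pre: 1 / √((1 + r)/2 + 1 − 2r) = 1 / √(1.5(1 − r)).
- Change contrast, post minus pre: 1 / √(2(1 − r)).

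At r = 0.6, persistent: 0.6667/√0.7333 = 0.7785 against 1/√0.6 = 1.2910, ratio 0.603. Post-only: 0.3333/√0.7333 = 0.3893 against 1/√0.8 = 1.1180, ratio 0.348.

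Ninety per cent power at two-sided .05 corresponds to z = 3.24. Multiplying by the ratio and converting back to power (at r = 0.6, persistent: 3.24 × 0.603 = 1.95, giving 50%):

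| r | Ratio, persistent | Power | Ratio, post-only | Power |
|---|---|---|---|---|
| 0.4 | 0.816 | 75% | 0.471 | 33% |
| 0.6 | 0.603 | 50% | 0.348 | 20% |
| 0.8 | 0.392 | 25% | 0.227 | 11% |

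**Step 3: where the loss begins.** For a persistent effect the two tests are equal when (4/3)/(1 + 2r) = 1/(1.5(1 − r)), so 2(1 − r) = 1 + 2r and r = 0.25. Below that, the pooled test is not the weaker one, although its estimate is still 2d/3. For a post-only effect, equality needs (2/3)(1 − r) = 1 + 2r, so r = −0.125; any non-negative correlation gives a loss.

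**Step 4: a check at a fixed size.** With an assumed 80 per arm and d = 0.50 SD, persistent, the pooled test has power 0.82, 0.73 and 0.65 at r = 0.3, 0.5 and 0.7. The change contrast has 0.87, 0.955 and 0.997. With pre as reference and the interaction kept, the group test rejects about 5% of the time, which is its alpha level.

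**The case against.** The strongest reply is that the general model is expressly carried forward to later aims and that the interaction is the stated decision rule for each aim. On that view, group condition in the hypothesis 3 paragraph is shorthand for a treatment effect already defined. This stands in part: it makes the model with no interaction the less natural reading, and it shows the wording to be inconsistent rather than a deliberate choice of another effect. It does not rescue the rule. Carrying the model forward supplies the interaction term, but the hypothesis 3 rule still names the group effect, and the general model writes the two coefficients separately. An analyst following the text could test either.

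A reader might infer four stronger things that the document does not support:

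- **That the first step can succeed only about 5% of the time.** This needs categorical occasion with pre as reference. The SAP fixes dummy coding for treatment group only; under sum coding the coefficient is again the two-thirds average.
- **That power always falls sharply.** For a persistent effect the loss is small at r = 0.3 (0.82 against 0.87 in the check above) and absent below about 0.25.
- **That chance baseline imbalance biases the rule.** Under randomisation such imbalance is ordinary type I error. Nor is it carried in full: with equal correlation, a pre-training difference enters the three-occasion mean as (1 + 2r)/3 of itself, or 2.2/3 = 0.73 at r = 0.6.
- **That hypothesis 3 cannot be answered at all.** In an illustrative simulation with full mediation (200 runs, assumed 80 per arm and 6 prompts per occasion), the rule still declared mediation in 39% of runs on the pooled group effect, against 78.5% on the post × group term. These rates are rough: the fitted model ignored occasion-level variation, and the interaction stayed significant with stress included in 20.5% of runs.

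The adjusted models do include baseline symptom severity and baseline perceived stress. They are sensitivity analyses run second, and the SAP gives them no different mediation rule.

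**Conclusion.** The point holds as a mismatch between the mediation rule and the plan's own definition of the treatment effect, with a loss of sensitivity under most plausible completions of the model. The dilution to 2/3 or 1/3 follows from balanced occasions alone under the pooled reading. The power figures also rest on the assumed equal variances and common correlation, and on a two-arm contrast. The zero-expectation result applies only if occasion is categorical with pre as reference and the interaction is kept.

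The problem is confined to the mediation statement. The interaction tests for treatment effects on stress and symptoms are not affected. It should still be settled before analysis, because this is the only stated rule for declaring mediation.

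**What to change.** In the hypothesis 3 paragraph, define the effect to be mediated as the change-from-pre contrast between MA-MBSR and each comparator, at post and at follow-up. Fit both mediation models, with and without stress, with occasion, group and occasion × group, and state how occasion is coded. Base the mediation statement on those contrasts, not on the group main effect. An acceptable alternative is to analyse post-training prompts only, adjusted for each person's pre-training mean, and to say so.

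The cost is a few sentences of SAP text and extra model terms; no new data are needed. This change does not resolve whether loss of significance is an adequate criterion for mediation, which is a separate question.

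### The hypothesis 3 mediation rule does not require its two models to use the same EMA prompts, so in the lagged form the group effect can lose significance, and mediation be declared, through fewer rows alone

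*SAP*

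**What the plan says.** All references are to the SAP, Data Analysis Strategy.

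- **Models compared** (Testing our Hypotheses, hypothesis #3). Both models have EMA symptom severity as outcome and group as a fixed effect; "one MLM will include stress as an additional fixed effect, and another will not".
- **Decision rule** (same paragraph). Mediation is concluded on this condition (the quote stops just before the sentence names stress as mediator): "If the fixed effect for group condition is statistically significant in the latter but not the former, stress reduction will be declared to act as".
- **Timing of stress** (same paragraph). "We will test for concurrent relations between EMA-sampled stress and IBS symptom severity (within the same moment) and also test lagged relations", the lagged version relating stress at one time point to symptoms at the next.
- **Data used** (the paragraph on mixed models that follows the overview). "MLMs provide an optimal analytic strategy because they model all available data". This is a general rationale, tied there to intention to treat. It is the only statement that bears on which rows a model uses.

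The SAP does not say which prompts enter either mediation model. It neither states that they differ nor requires that they match. It also does not say whether a lag may run from one day to the next.

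**The concern.** The rule reads a change in significance between two models as evidence about stress. That makes sense only if stress is the only thing that changed. In the lagged form, a prompt with no earlier stress value cannot enter the stress model, yet it stays in the model without stress if all available data are used. If lags stay within the day, the first prompt of each day is lost even with perfect compliance, and so is each prompt that follows a missed one.

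The stress model is therefore always the smaller of the two. Its group effect has a larger standard error and an estimate from a different set of rows. Either can push a p-value across .05, and the rule counts that as mediation. What is at stake is the mechanistic claim of hypothesis 3: it could be declared supported when stress is unrelated to symptoms.

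**Working it through.** **Inputs.** From the SAP: the two-model comparison, the significance rule, the lag, a random intercept for day within participant, and two-sided .05 (stated for the occasion-by-treatment interaction and assumed here for the mediation rule). The SAP gives no arm size, EMA days, prompts per day, prompt response rate, variance components or effect size. All of these are assumptions below. There is no figure in the plan to reproduce.

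**1. Rows lost.** With k prompts a day, all answered, and lags kept within the day, the lagged model loses 1/k of rows: 33%, 25%, 20% and 17% for k = 3, 4, 5, 6. If a share p of prompts is answered at random, it keeps p(k-1)/k of the answered prompts:
- k = 4, p = .65: .65 × 3/4 = 49%
- k = 6, p = .80: .80 × 5/6 = 67%

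**2. Standard error.** For D days, the variance of a participant's mean is τp + τd/D + s/(Dk), where τp, τd and s are the participant, day and moment shares. For the pre-to-post change, τp cancels. Lagging replaces k by k-1.

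Example with shares .4, .1, .5, D = 3 and k = 4:
- Group main effect: .4 + .0333 + .0417 = .4750 becomes .4 + .0333 + .0556 = .4889. SE ratio √(.4889/.4750) = 1.015.
- Change contrast: .0333 + .0417 = .0750 becomes .0333 + .0556 = .0889. SE ratio √(.0889/.0750) = 1.089.
- Power that was 80% becomes Φ(2.802/ratio - 1.960): 78.9% and 73.0%.

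Over D = 3-7, k = 3-6, participant share .2-.6, day share .1 and moment share .3-.7, with every prompt answered:

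| Tested term | SE ratio | 80% power falls to |
|---|---|---|
| Group main effect | 1.001-1.061 | 79.9%-75.2% |
| Change (occasion × group) | 1.033-1.162 | 77.4%-67.4% |

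**3. The rule applied at prompt level when stress has no effect on symptoms.** Generalised least squares with known variance components, two arms of 60, two occasions, shares .4, .1, .5, change contrast powered at about 80%. Treatment lowers stress by 0.3 unless noted. 600 runs per row, except 150 where marked. Rates are per trial simulated.

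| Setting | Total effect significant | Declared, all rows vs stress rows | Declared, identical rows |
|---|---|---|---|
| Lagged, D=3, k=4 | 79.7% | 11.0% | 2.5% |
| Lagged, D=5, k=5 | 80.2% | 9.2% | 1.3% |
| Lagged, D=3, k=4, treatment does not move stress | 80.2% | 11.7% | 0.7% |
| Lagged, D=3, k=4, 15% of stress values lost (150) | 82.0% | 16.7% | 3.3% |
| Concurrent, D=3, k=4, none missing | 81.5% | 0.7% | 0.7% |
| Concurrent, D=3, k=4, 5% of stress items lost (150) | 82.0% | 2.7% | 0.7% |

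Among trials with a significant all-row total effect, the four lagged rows become 11.0/79.7 = 13.8%, 9.2/80.2 = 11.5%, 11.7/80.2 = 14.6% and 16.7/82.0 = 20.4%. Monte Carlo error is about 1.3 points at 11% (600 runs) and about 3 points at 16.7% (150 runs).

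**4. A second simulation with random prompt non-response.** Two arms of 70, 3 or 7 days, 4 or 6 prompts, 65-80% answered, shares .40 person, .08 person-by-occasion, .08 day, .44 moment. Tests on participant means approximate the mixed model; 3,000 replicates; stress unrelated to everything. False declarations among trials with a significant total effect:

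| True effect | Change contrast | Group main effect |
|---|---|---|
| 0.25 SD | 5-37% | 4-15% |
| 0.40 SD | 0.1-12% | 3-9% |

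On identical rows the rate was at most 2.6%, checked for the change contrast only. For 3 days, 4 prompts, 80% answered and 0.25 SD, the rate was 19%. Repeat runs of that setting gave 18% and 19%, against 2% on identical rows. A repeat of the worst case gave 35%. At 0.4 SD with 7 days and 6 prompts, a repeat gave 0.1-0.4%.

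**The case against.** **The SAP is only silent.** A reader might infer that the plan has the two models fitted to different prompts. It does not say so, and analysts often use a common set when comparing nested models. This stands against the stronger reading. It does not remove the point: the SAP writes out a decision rule, and its one general statement on data leads, in the lagged form, to unequal rows.

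**The lag may not belong to the rule.** The SAP announces concurrent and lagged relations and then describes a single pair of models. That the pair is run with lagged stress is a reading, though the natural one, and nearly all the quantified harm depends on it.

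**The concurrent form is barely affected.** This stands. Both items come from the same moment, so rows differ only where stress is missing and symptoms are present, and the SAP gives no rate for that.

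**The rule names the group effect, not the change.** On that literal reading the excess is smaller. In repeat runs at 0.25 SD, false declarations were 1.1-3.2% of all trials, and flips in the opposite direction were about as common (0.7-3.3%), so much of it is noise around a threshold. No identical-row comparator was run for this term. The change reading nevertheless has support: the SAP evaluates the occasion-by-treatment interaction for each aim, carries its general model over to later aims, and frames hypothesis 3 as reduction and improvement.

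**Dropped rows do not bias the estimate.** Under the random non-response simulated, they add zero-mean noise. No systematic shift has been shown.

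**The rule itself is the larger defect.** This also stands. A change in significance does not test the indirect effect, even on identical rows.

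**Conclusion.** The point holds as an omission that lets the stated rule misfire in the lagged form. With stress unrelated to symptoms, false declarations among trials with a significant total effect range from about 0% (large effect, many prompts), through about 5-20% in intermediate settings, to the mid-30s% (few days, many missed prompts, change contrast). On identical rows the figure is about 0-3%.

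Every figure rests on assumed arm sizes, schedules, response rates, variance shares and effect sizes. The top of the range should not be read as the expected error in this trial. The excess is usually smaller for a group main effect, though not in every setting: at 0.40 SD the main-effect range starts higher (3%) than the change range (0.1%). It is negligible for the concurrent form when both items are always answered together.

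Two further inferences are not supported: that the SAP prescribes different row sets, and that matching the rows would make the mediation rule sound.

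**What to change.** Add to the hypothesis #3 paragraph under Testing our Hypotheses, in words such as:

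*For each mediation comparison (concurrent and lagged), both MLMs are fitted to the identical set of prompts, namely those with symptom severity and the stress value used in that comparison both observed. The numbers of prompts and participants are reported. The total effect on all prompts is reported separately and is not used to judge mediation.*

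The same paragraph should say whether the lagged form enters the rule, whether lags stay within the day, and whether the tested term is the group main effect or the occasion-by-group contrast.

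The cost is a few sentences and one filter in the code. The total effect in the mediation comparison becomes slightly less precise because it uses fewer prompts; the separate all-prompt estimate keeps the full data in view.

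If the significance rule is later replaced, the row restriction should carry over only to estimates based on the difference in group coefficients with and without stress. The working here gives no basis for imposing it on other indirect-effect estimates. The weakness of the significance comparison needs its own remedy.

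### Hypothesis 3 is decided by one three-arm group effect with no named contrast, so MO-MBSR can trigger or block a mediation verdict that should concern MA-MBSR

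*SAP*

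**What the plan says.** Under Testing our Hypotheses, the SAP sets out the comparisons of interest: "We are specifying a priori predictions about the effects of MA-MBSR intervention, relative to MO-MBSR and CC". For hypothesis 3 the aim is "to test whether EMA-sampled stress reduction will statistically mediate symptom improvements", with no arm named. The method is that "we will compare two MLMs that use IBS symptom severity as the outcome and group condition as a fixed effect", one model with stress and one without. The decision turns on a single condition, which leads to a declaration of mediation: "If the fixed effect for group condition is statistically significant in the latter but not the former, stress reduction will be declared to act as".

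Two other statements bear on what the group effect is. The analysis overview has three arms, and "Treatment groups will be dummy coded with CC (coping control) used as the reference group". The general model, which the SAP carries over to later aims, is judged by one omnibus test: "The primary test of hypothesis is the F-test of the null hypothesis" that the group-by-time term is zero. The overview also provides planned contrasts between unnamed groups at post-training, but only after a significant occasion-by-treatment interaction.

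**The concern.** Mediation belongs to a particular comparison. Stress may explain why MA-MBSR differs from CC without explaining why it differs from MO-MBSR, or the reverse. A rule that returns one verdict for three arms cannot separate these.

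There are two ways to read the rule:

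- **As a 2-df test of group.** Any pair can drive it, including MO-MBSR versus CC. After stress is added, any remaining difference between any two arms can keep it significant.
- **As single coefficients with CC as reference.** The coefficients are MA-MBSR versus CC and MO-MBSR versus CC. The SAP does not say which decides, and MA-MBSR versus MO-MBSR is not among them.

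Under either reading, the report could credit stress reduction as the mechanism when MA-MBSR did nothing. Under the 2-df reading, it could also deny mediation when stress carries the whole MA-MBSR benefit.

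**Working it through.** The SAP states no sample size, effect size or power for hypothesis 3, so there is no figure to reproduce. The check asks how often the rule declares mediation in situations where the truth for MA-MBSR is known.

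**Inputs.** From the SAP: three arms, and the two-model rule. The .05 two-tailed level is stated for the interaction test and is assumed here for the mediation rule. All else is assumed: 80 per arm; one stress change and one symptom change per person; an arm that acts on stress lowers it by 0.8 SD; stress-to-symptom slope 0.6; symptom residual SD given stress 0.8 or 1. This simplifies the 3-level EMA model to person level and does not cover the lagged analysis.

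**Closed-form check of the 2-df rule.**

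- Symptom shift through stress: 0.6 × 0.8 = 0.48.
- Within-arm symptom variance: 0.6² + 0.8² = 1.00, or 0.6² + 1² = 1.36.
- Noncentrality = n × Σ(arm mean − grand mean)² / variance. If only MO-MBSR works, the deviations are 0.16, 0.16 and −0.32, so it is 80 × 0.1536 / 1.00 = 12.29, or 12.29 / 1.36 = 9.04.
- Power of the unadjusted F-test (2 and 237 df): 0.887 or 0.767. With stress added, no group effect remains, so the adjusted test is non-significant in about 95%.
- Mediation declared: 0.887 × 0.95 ≈ 0.84, or 0.767 × 0.95 ≈ 0.73.

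The sum of squares is the same 0.1536 if only MA-MBSR works, or if both work equally through stress. The rule cannot tell these three situations apart.

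**Simulated rates, 2-df rule, 80 per arm.**

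| Truth | Residual SD 0.8 | Residual SD 1 |
|---|---|---|
| Only MO-MBSR works, through stress | 84% | 73% |
| Both MBSR arms work equally through stress | 85% | 75% |
| Only MA-MBSR works, wholly through stress | 85% | 73% |
| As the row above, plus MO-MBSR direct effect ±0.5 outside stress | 1-2% | 5-11% |

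In the second row the MA-MBSR versus MO-MBSR mediated effect is zero. In the last row the MA-MBSR benefit over CC is still wholly mediated, but the direct MO-MBSR effect keeps the adjusted group test significant.

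**Other assumptions** (shift 0.7, slope 0.6, residual SD 0.8, direct effect ±0.4). At 100 per arm: 82% if only MO-MBSR works (62% at 60 per arm, 93% at 150), 84% if only MA-MBSR works, and 3.2% (−0.4) or 4.8% (+0.4) in the blocked cases. On the single-coefficient reading, MO-MBSR versus CC alone triggers the rule in 81% when only MO-MBSR works.

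**Does naming the contrast suffice?** The first set of assumptions, keeping the significant/not-significant rule:

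- *MA-MBSR versus CC:* about 3% if only MO-MBSR works, and 71-83% in the blocked cases. Naming the contrast largely cures the problem.
- *MA-MBSR versus MO-MBSR:* still unsatisfactory. With residual SD 1, the rule declares mediation in 71% if only MO-MBSR works, where the difference favours MO-MBSR, and in 15% or 2% with a direct effect of +0.5 or −0.5. With −0.5 the total difference is −0.48 + 0.50 = 0.02, so the first step fails. With +0.5 it is −0.98, of which −0.50 remains after adjustment, so the second step usually fails. The stress-mediated part is −0.48 in both.

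**Testing the indirect effect for each contrast.** MA-MBSR versus MO-MBSR is detected in over 99% when only MA-MBSR works through stress, with or without the direct MO-MBSR effect, and flagged in 5% when it is zero. MA-MBSR versus CC is flagged in 5% when only MO-MBSR works. In that last case, however, the two-sided MA-MBSR versus MO-MBSR test is significant in about 100% of trials, always favouring MO-MBSR, so direction must be part of the criterion.

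**The case against.** Four points can be made for the plan.

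- **Hypothesis 3 names no arm.** If only MO-MBSR works and does so through stress, then stress does mediate the improvement that occurred, and the declaration is true as worded. This stands. A reader might infer from the 84% that the rule asserts mediation where none exists. The SAP does not support that: the error is in reading the verdict as one about MA-MBSR, which the general statement of predictions invites.
- **The contrasts are implied.** The overview provides planned contrasts in each model, and the hypotheses section refers to specified pairwise comparisons, so a sympathetic analyst might import the two MA-MBSR contrasts. That shows the intent, and it would be unfair to say that the plan ignores contrasts. But they follow an interaction test, the groups are unnamed, and the mediation rule does not use them.
- **The other results would show it.** If MA-MBSR did nothing, its comparisons under hypothesis 2 should say so. That would help a careful reader, but it would not correct the hypothesis 3 verdict. Nor does it help where stress carries the MA-MBSR benefit and the verdict is blocked.
- **The real fault is the loss-of-significance criterion.** This stands in part. For MA-MBSR versus CC, naming the contrast does most of the work. For MA-MBSR versus MO-MBSR it does not, and the criterion must go too. It would be wrong to infer that naming contrasts alone repairs the rule.

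**Conclusion.** The concern holds: following the rule as written can give a wrong answer for MA-MBSR, in either direction. Under the assumed inputs the 2-df rule declares mediation about as often when MA-MBSR is inert and MO-MBSR works (73-84%) as when MA-MBSR works wholly through stress (73-85%). It declares it in only 1-11% when MO-MBSR also has a direct effect of ±0.5.

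The direction follows from the structure of the rule. The rates do not: they depend on assumed effects, sample size and residual SD, and on a person-level simplification. They should not be quoted as this trial's error rates.

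**What to change.** In the hypothesis 3 text under Testing our Hypotheses:

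1. Replace the verdict on the group effect with the stress-mediated (indirect) effect and its confidence interval, for each of two named contrasts: MA-MBSR versus MO-MBSR and MA-MBSR versus CC. Using MA-MBSR as the reference level in the mediation models gives both directly.
2. Declare hypothesis 3 supported for a contrast only if its interval excludes zero in the direction favouring MA-MBSR, that is, lower stress leading to lower symptoms.
3. State that a claim relative to both comparators needs both contrasts to succeed. This needs no split of alpha.
4. Report MO-MBSR versus CC as exploratory.

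The cost is SAP wording and a change of reference level, with no new data or participants. The downside is that a full claim must succeed on two contrasts, so it is somewhat harder to reach than a single pooled verdict.
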